1 STUDY SYNOPSIS

310D1 31NOP313	
Complete Protocol Title	Anatomical Shoulder [™] Inverse/Reverse Post-Market Surveillance Study A Multicenter, non-comparative, prospective post-market surveillance study to obtain clinical and radiographic outcome data on the Anatomical Shoulder [™] Inverse/Reverse System when used in primary total shoulder replacement
Protocol Number	06-U02
Short Protocol Title	Anatomical Shoulder [™] Inverse/Reverse study
Sponsor	Zimmer GmbH, [name], Switzerland
Manufacturer	Zimmer Switzerland Manufacturing GmbH, [name], Switzerland
Study Device(s)	Anatomical Shoulder [™] Inverse/Reverse system
Study Objectives/Endpoints	The objectives of this study is to obtain outcome data on the Anatomical Shoulder TM Inverse/Reverse system by analysis of standard scoring systems and radiographs.
Indications/Target Population	When there is severe distortion of osseous anatomy and loss of normal cuff tendon structure, reconstruction in order to restore function and offer pain relief is possible using the Anatomical Shoulder TM Inverse/Reverse system.
Inclusion/Exclusion Criteria	 Age - 18 years minimum. Sex - male and female. General Health - the patient should be able to undergo surgery and participate in a follow-up program based upon physical examination and medical history. Informed Consent - patient or patient's legal representative has signed a 'Patient Informed Consent form' Indications - Diagnosis of disease or trauma in the affected joint, including Cuff-tear arthropathy Failure of prior rotator cuff surgery Irreparable rotator cuff tears associated with loss of glenohumeral stability with the indication for total shoulder arthroplasty.

	- The deltoid muscle has to be intact in all 3 parts (clavicular, acromial as well as spinal).
	Exclusion Criteria:
	Patient is skeletally immature.
	Patient is pregnant.
	 Patient is unwilling or unable to cooperate in a
	follow-up program.
	 Patient shows one of the following medical conditions:
	- Chronic fracture
	- Acute fracture
	- Axillary nerve lesion
	- Severe loss of humeral or glenoid bone
	- Paralysis of the deltoid muscle
	- Active Infection
	 Patient requires one of the following medical interventions:
	- Implant revision
	- Glenoid bone grafting
	- Auto grafts
Study Design	A multicenter, non-comparative, prospective post- marketing study.
Clinical Phase	Post-market
Sample Size	Maximum of 160 study subjects implanted with the study device.
Length of Study	11 years (1 year patient recruitment and 10 year follow-up period). Follow-up evaluations are conducted at 6 weeks and thereafter at 1,2,5 and 10 years post hospital discharge.
Materials and Methods	Case report forms will be completed either in-office or hospital at Pre-op, Surgery, Discharge, and at the 6 week/6months and at 1, 2, 5 and 10 year post-operation intervals.
Data Collection	Paper/Electronic
Statistical Reporting	Data collected will be summarized and reported to each participating investigator. Statistical analysis will be conducted by Zimmer Biomet or its designee. Survivorship will be evaluated using Kaplan-Meier.

Scores/Performance Assessments	Constant-Murley Score, Revisions, Adverse Events, Radiographic Assessment.
Standards	 The PMCF is compliant with the below: ISO 14155: 2020 - Clinical investigation of medical devices for human subjects - Good clinical practice. The Declaration of Helsinki (DoH) – Ethical principles for medical research involving human subjects. European Regulation (EU) 2017/745.
Study Funding	Funding for this clinical study is made available by Zimmer Biomet to support clinical data collection, IRB/EC review fees and other expenses associated with the conduct and execution of this study protocol as outlined in the fully executed Clinical Trial Agreement.

2 STATISTICAL ANALYSIS PLAN

2.1 Statistical Considerations

Data collected in the study will be summarized descriptively. Descriptive summaries will be the basis of study reports to participants, as well as to generate an overall summary of the clinical performance of the various implants captured within the database and may be used for reports and to support presentations and publications as needed.

Summaries will routinely describe categorical data as counts and percentages, and ninety-five percent confidence limits will be generally used to assess differences between different implant configurations. Routine summaries describing continuous data will be in the form of means, medians, standard deviations, minima, and maxima, and ninety-five percent confidence intervals will be used to contrast differences.

Routine summaries of implant survival, return to function, etc. (e.g. time to event) will generally be described via the Kaplan-Meier method and these will generally be accompanied with the corresponding crude rates (expressed as percentages). Routine summaries of complication data will be in the form of frequencies and percentages. Summaries may be further generated for strata within the study population, (e.g. males and females, at different cut-points in the body mass index continuum, etc.).

Patient confidentiality will be protected at all times, and patient identifiers will not be included in study summaries.

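### Does section 2.1 need a planned interval for implant survival, and a competing-risk estimate of the proportion revised?

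*Combined protocol and SAP*

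**What the plan says.** The synopsis describes a "Multicenter, non-comparative, prospective post-market surveillance study" with a "Maximum of 160 study subjects implanted with the study device". On survivorship its statistical entry says only: "Survivorship will be evaluated using Kaplan-Meier". Revisions are one of four listed assessments.

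Section 2.1 gives the method: "Routine summaries of implant survival, return to function, etc. (e.g. time to event) will generally be described via the Kaplan-Meier method". It adds that "these will generally be accompanied with the corresponding crude rates (expressed as percentages"). It names no event, does not say how deaths are treated and gives no denominator for the percentage.

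Section 2.1 mentions 95% limits twice. For categorical data, "ninety-five percent confidence limits will be generally used to assess differences between different implant configurations". For continuous data, "ninety-five percent confidence intervals will be used to contrast differences". Neither statement covers the survival curve. Section 2.2 deals with continuous and categorical data only, and its two-sided 0.05 level applies to comparisons of scores before and after surgery.

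**The concern.** Two things look wrong.

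- **No interval.** In a single-group study the survival figure stands alone, yet both 95% statements concern differences. With at most 160 patients and 10 years of follow-up, a bare survival percentage could look far more certain than it is. Section 2.1 allows the summaries to be used in presentations and publications.
- **No estimate of the proportion revised that allows for both death and loss.** Kaplan-Meier with deaths censored estimates net implant survival, that is, survival of the implant with death set aside. One minus that figure exceeds the share of patients revised once some patients die. A crude percentage over all implanted patients keeps deaths in the denominator but is too low when patients are lost. With both deaths and losses, the two planned figures fall on either side of the proportion revised.

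**Working it through.** **Inputs.** From the documents: at most 160 implanted patients and 10 years of follow-up. The documents give no rates of revision, death or loss, and no precision target, so there is no figure of the plan's own to reproduce. Assumed: constant yearly rates r (revision), d (death) and l (loss), with T = r + d + l. Also assumed, following usual convention: deaths and losses are censored in Kaplan-Meier, and the crude percentage is taken over all implanted patients.

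**Formulas at t years, n = 160.**
- 1 - KM = 1 - exp(-rt)
- Cumulative incidence of revision, death competing = r/(r+d) × [1 - exp(-(r+d)t)]
- Crude percentage = r/T × [1 - exp(-Tt)]
- Expected number at risk = n × exp(-Tt)
- V = r × [exp(Tt) - 1]/(nT), and 95% half-width = 1.96 × exp(-rt) × √V

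**Case A: r = 1%, d = 4%, l = 5%, t = 10.** This is a high-loss case: 5% a year alone implies 1 - exp(-0.5) = 39% lost over 10 years.
- 1 - KM = 1 - exp(-0.10) = 9.5%
- Cumulative incidence = 0.2 × [1 - exp(-0.5)] = 7.9%, so the gap is 1.6 points
- Crude = 0.1 × [1 - exp(-1)] = 6.3%, about 20% too low relative to 7.9%
- At risk = 160 × exp(-1) = 59
- V = 0.01 × 1.718/16 = 0.00107 and √V = 0.0328, so the half-width is 1.96 × 0.905 × 0.0328 = 5.8 points
- Log-log limits: 1.96 × 0.0328/0.10 = 0.642, and 1 - exp(-0.10 × exp(±0.642)) gives 5.1% and 17.3%

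**Case B: the same with l = 3%.** The gap does not depend on loss and stays at 1.6 points. V = 0.01 × 1.226/12.8 = 0.00096, giving a half-width of 5.5 points. Crude = 0.125 × [1 - exp(-0.8)] = 6.9%, about 13% too low.

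**Lower loss.** At 1% a year the crude shortfall is 4.4%. With no loss it is zero and crude equals the cumulative incidence.

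**Gap against precision.** In case A, 1.6/5.8 = 0.28, and in case B, 1.6/5.5 = 0.30. At 5 years in case A the gap is 0.45 points against a half-width of 3.75, or 0.12. Over the 18 combinations of r = 0.5, 1, 2%, d = 2, 4, 6% and l = 3, 5%, the 10-year half-width runs from 3.8 to 8.1 points and the gap from 0.5 to 4.4. The ratio never exceeds 0.57.

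**Different assumptions.** Take 10-year implant survival of 90% or 95%, 20-40% of patients dead and 0-30% lost. The expected interval is then about 8 to 12 points wide, and 1 - KM is 1.11 to 1.27 times the cumulative incidence.

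**Data needed for the extra curve.** The competing-risk estimate works only if deaths are told apart from losses. In case A, if half the deaths are recorded as losses, it gives (0.01/0.03) × [1 - exp(-0.3)] = 8.6%. If all are, it gives 9.5%, which is 1 - KM again. The schedule is stated as: "Follow-up evaluations are conducted at 6 weeks and thereafter at 1,2,5 and 10 years post hospital discharge". No visit falls between 5 and 10 years, and the documents do not describe any ascertainment of vital status.

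**The case for a change.** The strongest case for a change concerns the interval. A plan should commit to the precision of its main single-group estimate, one sentence would do it, and leaving matters to what is generally done is not a commitment. In case A, reported survival of 90.5% is compatible with roughly 83% to 95%, and a reader cannot see that without limits and numbers at risk.

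Much of this stands as fact: no sentence promises an interval, no redaction explains the silence, and the uncertainty is wide. What does not follow is that the plan would produce a wrong or misleading estimate. Section 2.1 is written as a set of reporting defaults and excludes nothing. Limits and numbers at risk are a routine part of a Kaplan-Meier analysis, and supplying them alters no estimate.

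The case on the proportion revised is weaker. The synopsis and section 2.1 name survivorship and implant survival, and no passage asks for the 10-year proportion of patients revised. The direction of bias also depends on conventions the documents leave open. If the crude percentage is taken over patients of known status, it is 8-23% too high in the 18 combinations instead of too low. That makes it a matter of definition for the analyst to state, not a demonstrated bias in the plan.

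**Conclusion.** No change to the plan follows. Kaplan-Meier is a sound estimator of the quantity the plan names, provided deaths are censored and death is unrelated to revision risk. The missing interval, numbers at risk, event definition, death handling and crude denominator are gaps in reporting detail that a competent analyst fills when producing the tables.

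A cumulative incidence curve is a reasonable optional extra if deaths are recorded separately from losses. On the assumed rates it would move the 10-year figure by 0.5 to 4.4 points, always less than the half-width of the Kaplan-Meier estimate (3.8 to 8.1 points). All these sizes rest on assumed constant rates. The conclusion itself rests on the stated target being implant survival and on no test, target or sample size depending on the point.

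### Section 2.1 gives 10-year complication percentages no denominator and no allowance for unequal follow-up; state the denominator and add cumulative incidence of first complication (minor, cheap improvement)

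*Combined protocol and SAP*

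**What the plan says.** Section 2.1 deals with two kinds of outcome in consecutive sentences. For the first: "Routine summaries of implant survival, return to function, etc. (e.g. time to event) will generally be described via the Kaplan-Meier method", with crude percentages shown alongside. For the second: "Routine summaries of complication data will be in the form of frequencies and percentages". The Statistical Reporting row of the synopsis names the time-to-event method for one outcome: "Survivorship will be evaluated using Kaplan-Meier". Section 2.2 adds only frequency and percentage for categorical data.

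The Length of Study row gives the schedule: "Follow-up evaluations are conducted at 6 weeks and thereafter at 1,2,5 and 10 years post hospital discharge". Sample Size is "Maximum of 160 study subjects implanted with the study device". The listed assessments are "Constant-Murley Score, Revisions, Adverse Events, Radiographic Assessment". Section 2.1 also says that the descriptive summaries "may be used for reports and to support presentations and publications as needed".

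No section gives the denominator for complication percentages, a person-time or cumulative-incidence method for complications, or a rule for patients who die or are lost before 10 years.

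**The concern.** A complication percentage reported after 10 years will be read as the chance of a complication within 10 years. It has that meaning only if every patient is followed until a complication, death or year 10. Once patients drop out, the figure depends on who is in the denominator. Counting everyone implanted treats a patient lost at year 2 as free of complications to year 10. Counting only patients with an event or complete follow-up removes event-free patients but keeps the events, which pushes the figure up.

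The plan already uses a time-to-event method for implant survival over the same period, so leaving complications without one is a gap and not a general policy. At stake is the accuracy of a descriptive safety figure in a single-arm surveillance study whose summaries may be published. No decision rule in the documents turns on it.

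**Working it through.** **Inputs from the documents.** Follow-up 10 years; at most 160 patients; complications as counts and percentages. There is no planned figure to reproduce: the documents give no complication, death or loss rate and no derivation of 160. All rates below are assumptions.

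**Step 1: all-implanted denominator.** Let r, d and l be yearly hazards of first complication, death and loss, independent of one another and constant within an interval of length w. S is the share still at risk when the interval starts. Each interval contributes

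S × r/(r+h) × (1 − exp(−w(r+h))).

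With h = d this sums to the actual 10-year cumulative incidence. With h = d + l it sums to the expected percentage over all implanted patients.

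Constant r = 0.02, d = l = 0.04:
- cumulative incidence = 0.02/0.06 × (1 − e^−0.6) = 15.04%
- all-implanted percentage = 0.02/0.10 × (1 − e^−1.0) = 12.64%
- gap = 2.40 points

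Front-loaded r = 0.08 in year 1, then 0.01, same d and l:
- cumulative incidence = 0.08/0.12 × (1 − e^−0.12) + e^−0.12 × 0.01/0.05 × (1 − e^−0.45) = 7.54 + 6.43 = 13.97%
- all-implanted percentage = 0.08/0.16 × (1 − e^−0.16) + e^−0.16 × 0.01/0.09 × (1 − e^−0.81) = 7.39 + 5.26 = 12.65%
- gap = 1.32 points

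All cases:

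| Complication hazard | d = l | All-implanted % | Cumulative incidence % | Gap (points) |
|---|---|---|---|---|
| 0.02 throughout | 0.04 | 12.64 | 15.04 | 2.40 |
| 0.08 in year 1, then 0.01 | 0.04 | 12.65 | 13.97 | 1.32 |
| 0.16 in year 1 only | 0.04 | 14.22 | 14.50 | 0.28 |
| 0.02 throughout | 0.02 | 15.04 | 16.48 | 1.44 |
| 0.08 in year 1, then 0.01 | 0.02 | 13.97 | 14.75 | 0.78 |
| 0.16 in year 1 only | 0.02 | 14.50 | 14.64 | 0.14 |

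Setting l = 0 makes the two formulas identical, so death alone does not bias the all-implanted percentage. The gap also nearly closes when complications come early.

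**Step 2: denominator of patients with an event or complete follow-up.** Take a true 10-year risk of 10%, no deaths and 20% loss. Then r = −ln(0.9)/10 = 0.01054 and l = −ln(0.8)/10 = 0.02231. Observed events are r/(r+l) × (1 − 0.9 × 0.8) = 8.98% of those implanted, and event-free completers are 0.9 × 0.8 = 72.00%. The percentage is 8.98/(8.98 + 72.00) = 11.1%. At 40% loss it is 7.87/(7.87 + 54.00) = 12.7%. The same data over all implanted patients give 9.0% and 7.9%. The choice of denominator alone moves the figure by 2.1 and 4.8 points.

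**Step 3: which estimator to add.** One minus Kaplan-Meier would be the wrong addition if patients die. Keep the hazard that gives 10% without death, and add a death hazard of −ln(0.7)/10 = 0.03567 (30% by 10 years). The actual cumulative incidence is 0.01054/0.04620 × (1 − 0.9 × 0.7) = 8.44%, while one minus Kaplan-Meier still targets 10%. Aalen-Johansen targets 8.44%.

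**Step 4: against sampling error.** Simulation of the Aalen-Johansen estimate at 160 patients (4,000 runs) gave 95% half-widths of 5.4 to 6.0 points for complications. A simple binomial check at 15% agrees: 1.96 × √(0.15 × 0.85/160) = 5.5 points. Every gap in Step 1 is smaller.

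**The case against.** The case against acting is reasonable. The sentence describes routine summaries and excludes nothing further, and the open-ended wording of the time-to-event sentence might be stretched to complications. The study is descriptive, its stated objective concerns scores and radiographs, and patients unwilling or unable to cooperate with follow-up are excluded. All rates above are assumed, and the understatements lie inside sampling error. Most of this stands, and it is why the priority is low. It does not remove the point: complications have their own sentence with their own method, and a confidence interval around a crude percentage does not allow for a shift caused by loss.

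A reader might infer more than the documents support:

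- *That the plan flatters the device.* The direction depends on a denominator that is not stated. It is downward over all implanted patients and upward over those with an event or complete follow-up.
- *That the 3- and 5-year gaps between late visits bias the percentage.* They do not; loss does. Long gaps matter more to the remedy, which needs onset dates.
- *That the actual revision risk lies between the two figures planned for implant survival.* This fails under some denominators. With revision hazard 0.01 and d = l = 0.04, the actual risk is 7.87% and one minus Kaplan-Meier is 9.52%. A crude rate over patients revised, dead or followed to 10 years is 6.59/73.63 = 8.96%, so the actual risk is below both figures. Over those revised or followed to 10 years it is about 14.0%.
- *That Kaplan-Meier for implant survival is an error.* With unrevised deaths censored it is a valid net survival summary. Preferring cumulative incidence of revision is a choice of estimand.

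**Conclusion.** The point holds for complications. As written, the percentage has no defined denominator and takes no account of unequal follow-up, so it need not estimate 10-year risk. Under assumed death and loss of 2% to 4% a year each, the all-implanted version is 0.1 to 2.4 points too low. The version over patients with an event or complete follow-up is 1.1 to 2.7 points too high for a true 10%, with 20% to 40% loss and no deaths. With no loss the percentage is right. These sizes rest on assumed rates and on loss being independent of complication risk; the true size cannot be derived from the documents. This is a cheap improvement of minor priority and does not invalidate the study.

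**What to change.** In section 2.1:

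1. State that complication counts and percentages use all implanted patients, and report the number still followed at each visit.
2. Add the Aalen-Johansen cumulative incidence of first complication at 1, 2, 5 and 10 years, with 95% confidence interval and number at risk. Report any complication, and individual types only where there are enough events. Treat death as a competing event, and revision as competing where it removes the implant at risk. Censor loss at last contact.
3. State the assumption that loss is unrelated to complication risk. Censoring does not cure informative loss, but it asks less than treating every lost patient as complication-free to 10 years.
4. Keep Kaplan-Meier for implant survival, labelled as net survival with unrevised deaths censored. Cumulative incidence of revision is optional.

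The cost is a little more analysis with a standard routine, and dates of complication onset, death and last contact. Onset dates need care because visits are far apart late in follow-up. The complication figure may look slightly less favourable than the all-implanted percentage.

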2.2 Statistical Analysis

Continuous data (e.g. age, BMI, Constant & Murley Score) will be reported using mean, standard deviation, median, and range. Comparisons between continuous baseline and interim patient visits will be performed using standard statistical tests and will be chosen as appropriate for the scale and distribution of the measures being analyzed. For example, a t-test, Wilcoxon test, or one-way ANOVA (as appropriate) may be performed to assess differences. Comparisons between preoperative and follow-up visit scores will use two-sided comparisons with α = 0.05, with no adjustment for multiple comparisons.

Categorical data (e.g. gender) will be reported using frequency and percentage. Comparisons between categorical baseline and interim patient visits will be performed using standard statistical tests and will be chosen as appropriate for the scale and distribution of the measures being analyzed.
